4 TRIAL DESIGN

4.1 Summary of Trial Design

This is a randomized, open-label, single centre, Phase 2 trial of RTS,S/AS01 in healthy Thai adults.

4.2 Primary Outcome Measures

The primary outcome measures will be:

- The safety of the investigational vaccine in each group:
 - Occurrence of serious adverse events (SAEs) from the date of the first vaccination to 29 days after the last vaccination, according to the MedRA classification.
 - Occurrence of SAEs during the whole study period, i.e. during a 6 month follow up period from the receipt of first vaccination, according to the MedRA classification.

- For groups 1 to 6, the concentration of antibodies against *Plasmodium falciparum* circumsporozoite (anti-CS antibody), one month after the first dose (at Study month 1), one month after the second dose (at Study month 2), one month after the third dose (at Study Month 3) and six months after the first dose (at Study Month 6).
- For group 7, the concentration of antibodies against *Plasmodium falciparum* circumsporozoite (anti-CS antibody), one month after the first dose (at Study month 1), two months after the first dose (at Study month 2), one month after the second dose (at Study month 3), and six months after the first dose (at Study Month 6).

4.3 Trial Participants

4.3.1 Overall Description of Trial Participants

190 healthy, non-pregnant Thai adults (aged 18 to 55 years, inclusive) will be recruited into the study.

4.3.2 Inclusion Criteria

The participant may enter the study if all of the following apply:

- Participant is a healthy male or non-pregnant female, aged 18 to 55 years (inclusive), of Thai origin.
- Participant is willing and able to give informed consent to participate in the trial
- Able, in the investigators opinion, and willing to comply with the study requirements and follow-up.

4.3.3 Exclusion Criteria

The following criteria should be checked at the time of study entry. If ANY exclusion criterion applies, the subject must not be included in the study:

- Female participant who is pregnant, lactating or planning pregnancy during the course of the study.
- Presence of any condition which in the judgment of the investigator would place the participant at undue risk or interfere with the results of the study (e.g. serious underlying cardiac, renal, hepatic or neurological disease; severe malnutrition; congenital defects or febrile condition).
- Hepatitis B surface antigen (HBsAg) detected in serum.
- Screening ECG demonstrates a QTc interval ≥ 450 ms

- Seropositive for hepatitis C virus (antibodies to HCV) at screening (unless has taken part in a prior hepatitis C vaccine study with confirmed negative HCV antibodies prior to participation in that study, and negative HCV RNA PCR at screening for this study).
- Anaemia (Hb < 10 g/dL)
- Positive malaria parasitaemia at screening or baseline (Month 0, Day 0).
- Use of any investigational or non-registered product or investigational use of a registered product (drug or vaccine), other than the study vaccines, during the period from the date of screening to the first vaccination, or planned use during the study period.
- Any medical condition that in the judgment of the investigator would make intramuscular (IM) injection unsafe.
- Any medical condition that in the judgment of the investigator would make the administration of the antimalarial treatment unsafe, such as prior allergic reactions to one or more component of the drug regimen: artemisinin, piperazine or primaquine.
- Contraindications to the use of artemisinin, piperazine or primaquine or use of medications known to have a potentially clinically significant interaction with these medications.
- Chronic administration (defined as more than 14 days in total) of immunosuppressants or other immune-modifying drugs during the period starting six months prior to the first vaccine dose. For corticosteroids, this will mean prednisone > 20 mg/day (for adult subjects), or equivalent. Inhaled and topical steroids are allowed.
- Planned administration/administration of a vaccine not foreseen by the study protocol in the period starting seven days before the first dose.
- Concurrently participating in another clinical study, at any time during the study period, in which the subject has been or will be exposed to an investigational or a non-investigational vaccine/product.
- History of splenectomy.
- Any confirmed or suspected immunosuppressive or immunodeficient condition, including HIV infection or based on medical history and physical examination.
- History of anaphylaxis post-vaccination.
- Serious chronic illness.
- Any abnormal baseline laboratory screening tests: ALT, AST, creatinine, haemoglobin, platelet count, total WBC, out of normal range as defined in the protocol.
- Hepatomegaly, right upper quadrant abdominal pain or tenderness.
- Personal history of autoimmune disease.
- Administration of immunoglobulins and/or any blood products during the period starting three months before the first dose of study vaccine or planned administration during the study period.

4.4 Indications for deferral of vaccination

The following events constitute contraindications to administration of RTS,S/AS01 at that point in time. If any one of these adverse events (AEs) occurs at the time scheduled for vaccination, the participant may be vaccinated at a later date, or withdrawn at the discretion of the investigator.

- Acute disease at the time of vaccination (acute disease is defined as the presence of a moderate or severe illness with or without fever). All vaccines can be administered to persons with a minor illness such as diarrhoea, mild upper respiratory infection with or without low-grade febrile illness, i.e. Axillary temperature <37.5°C).
- Axillary temperature of $\geq 37.5^{\circ}\text{C}$ at time of vaccination.
- Administration of a vaccine not foreseen by the study protocol within 30 days of any dose of RTS,S/AS01 with the exception of vaccines against polio, diphtheria, tetanus, pertussis, hepatitis B, *Haemophilus influenzae* type b, BCG, measles, influenza, pneumococcal disease or yellow fever which may not be given within one week of vaccination.

4.5 Absolute contraindications to further vaccination

The following AEs constitute absolute contraindications to further administration of RTS,S/AS01. If any of these AEs occur during the study, the participant must not receive additional doses of RTS,S/AS01, but may continue other study procedures at the discretion of the investigator. It is expected that the participant would continue full safety monitoring procedures, as per protocol.

- Acute allergic reaction or anaphylactic shock following the administration of vaccine investigational product.
- Pregnancy
- Any other findings that the investigator feels would increase the risk of having an adverse outcome from participation in the trial.

4.6 Expenses and Benefits

Reasonable compensation (e.g. for transport, parking, and lost working time) for any study visits will be reimbursed as appropriate. Subjects will receive compensation of 1,000 Baht for each scheduled study visit.

	group 1, 2, 3, 5	group 4, 6	group 7
screening	1,000	1,000	1,000
vaccination	3,000	3,000	2,000
antimalarials day 2 and 3		6,000	4,000
follow up	5,000	5,000	4,000

total	9,000	15,000	11,000
-------	-------	--------	--------

No direct benefit is foreseen from study participation. Meals to be provided to study participants at some study visits might be considered as a direct benefit and other possible indirect benefits may be possible since subjects will be screened for human immunodeficiency virus (HIV), hepatitis B and C and will receive a medical check-up. Knowledge gained from this study is may assist with the development of a vaccine against *P.falciparum* malaria which could potentially be used to help stop the spread of malaria and anti-malarial resistance in the region.

4.7 Potential Risks for Study Participants

4.7.1 Phlebotomy

There may be minor bruising, local tenderness or pre-syncope symptoms associated with venepuncture, which will not be documented as AEs if they occur.

4.7.2 RTS,S/AS01 vaccination

The most frequent adverse reactions observed in previous clinical trials using the RTS,S antigen and AS01 adjuvant system include pain, swelling, erythema, and tenderness at the site of injection, and systemic symptoms such as low-grade fever and short-term flu-like symptoms: fatigue, myalgia, headache, malaise. As with any vaccine, unexpected serious adverse events, including severe allergic reactions to the vaccine components, may occur, although this has not been reported in prior studies with RTS,S or the adjuvant in adults. In order to mitigate this risk, volunteers will be vaccinated in a clinical area where Advanced Life Support trained physicians, equipment and drugs are immediately available for the management of any immediate post-vaccination serious adverse reactions. Subjects will be observed closely for at least 30 minutes following administration of the vaccine.

Febrile seizures assessed as related to RTS,S/AS01 vaccination have been reported in children, but not in adults.

In the large Phase III study of RTS,S in infants and children in sub-Saharan Africa, an imbalance of meningitis cases of any aetiology (i.e. including cases with confirmed aetiology and cases with no aetiology found), with no cluster in time-to-onset, has been observed in children 5-17 months of age at first dose. Meningitis has not been a safety concern in RTS,S studies in adults.

Potential immune-mediated disease (pIMD) is a theoretical concern with adjuvanted vaccines. Some individuals vaccinated with adjuvant components identical to those that will be used in this study have reported autoimmune diseases (AID). A causal association between the adjuvant components and occurrence of autoimmune diseases has however not been established, as these can occur in people

who get other vaccines, or no vaccines at all. A meta-analysis of a GSK Vaccines adjuvanted vaccine showed no increased risk of AID associated to the adjuvant.

Meningitis and pIMDs are adverse events (AE) of specific interest.

4.7.3 Antimalarial medications

Dihydroartemisinin/piperaquine (DHA-PIP)

DHA-PIP is the first line treatment for uncomplicated malaria in many malaria endemic countries in Asia and Africa and has an extraordinary robust safety profile¹¹⁻³⁴. DHA-PIP is also very well tolerated. The main reported side effects are gastrointestinal upset (nausea, vomiting, abdominal pain and diarrhoea) as well as dizziness, headache and disturbed sleep. Rates of these side effects are generally < 10% and often <5% except for dizziness (~12%). There is no evidence that DHA-PIP can cause clinically significant QTc prolongation at therapeutic doses. To exclude the possibility that pre-existing QTc prolongation results in AEs, the QTc of all volunteers will be measured and candidates with a QTc_≥450ms will not be enrolled.

Primaquine (PQ)

Like all 8-aminoquinolones, primaquine is associated with haemolysis in G6PD deficient individuals in a dose-related relationship. To avoid any potential risk for haemolysis, participants will receive just a single low dose of primaquine (approximately 0.25mg/kg) on the day of vaccination, at each vaccine dose (groups 4, 6, and 7, only). This dose is safe even when administered to individuals with a genotype associated with severe G6PD deficiency. Other known side effects with primaquine administration include symptoms of gastritis and enteric complaints when administered for 14 days at large doses for the treatment of *Plasmodium vivax* malaria. Such abdominal complaints have not been observed when a single low dose primaquine is administered^{35, 36}.

Dosing Schedule

Bodyweight in kilograms	Number of tablets	
	(1 tablet contains 40mg DHA and 320 mg PIP)	(1 tablet contains 15mg primaquine)
41 - 50	2.5	0.5
51 - 60	3	1.0
61 - 70	3.5	1.0
71 - 84	4	1.5
85 - 100	5	2.0

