5.1.2 Anti-malarial therapy

Participants in Groups 4 and 6 will receive three rounds of antimalarial drugs - each round starting on the day of vaccination (Day 0) at Study Months 0, 1 and 2. Participants in Group 7 will receive two rounds of antimalarial drugs – each round starting on the day of vaccination (Day 0) at Study months 0 and 2. Each round consists of three daily doses of co-formulated dihydroartemisinin/piperaquine on Day 0, 1, and 2 (i.e. the day of vaccination and each day for 2 days after). Dihydroartemisinin/piperaquine tablets (Guilin Pharmaceutical Company or Sigma Tau Pharmaceuticals) for adult patients each contain 40mg dihydroartemisinin and 320mg piperaquine with a therapeutic dose range between 2–10 mg/kg/day dihydroartemisinin and 16–26 mg/kg/dose piperaquine. In addition each participant will receive a single low dose primaquine on the day of vaccination (Day 0). One single low dose primaquine of approximately 0.25mg/kg (Thai Government Pharmaceutical Organisation) will be administered. This drug regimen has been used in mass drug administrations in more than 10,000 participants which have established that this antimalarial drug regimen is safe and effective.

In the unexpected event that volunteers are found to be infected with malaria during screening, baseline or during follow-up examination they will be treated according to the most up-to-date government guidelines.

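### The 85–100 kg row of the section 4.7.3 dosing table gives 30 mg primaquine (0.300–0.353 mg/kg), 20–41% above the stated dose of about 0.25 mg/kg, although the table's own 1.5-tablet step is nearer at every weight in that band

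*Protocol*

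**What the plan says.** Section 4.7.3 (Antimalarial medications) describes primaquine haemolysis in G6PD-deficient people as dose-related. It then sets the protective measure for Groups 4, 6 and 7: "participants will receive just a single low dose of primaquine (approximately 0.25mg/kg) on the day of vaccination". The next sentence gives the assurance: "This dose is safe even when administered to individuals with a genotype associated with severe G6PD deficiency".

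Section 5.1.2 (Anti-malarial therapy) repeats the dose: "One single low dose primaquine of approximately 0.25mg/kg (Thai Government Pharmaceutical Organisation) will be administered". Neither section gives an accepted mg/kg range or a rounding rule for primaquine.

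The dosing table in 4.7.3 converts this into tablets by weight band, with the column header stating that "1 tablet contains 15mg primaquine". The primaquine entries are 0.5 tablet at 41–50 kg, 1.0 at 51–60 kg, 1.0 at 61–70 kg, 1.5 at 71–84 kg and 2.0 at 85–100 kg.

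**The concern.** The text and the table prescribe the same dose in two ways, and in the top band they disagree by more than half-tablet rounding requires. Staff will dose from the table, so the table decides what participants receive.

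The direction of the discrepancy gives it weight. The protocol relies on a low dose to avoid haemolysis, and section 4.8.7 lists no G6PD test. Its safety sentence refers back to about 0.25 mg/kg. A participant in the top band receives more than that in each round: three rounds in Groups 4 and 6, two in Group 7. These are healthy volunteers, and section 4.6 foresees no direct benefit from taking part.

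**Working it through.** **Inputs.** Target 0.25 mg/kg (sections 4.7.3 and 5.1.2); tablet strength 15 mg, weight bands and tablet counts (table in 4.7.3).

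**Formulas.** Delivered mg/kg = tablets × 15 ÷ weight. Target mg = 0.25 × weight. Deviation = delivered ÷ 0.25 − 1. The nearest half-tablet step is the one that minimises |15 × tablets − 0.25 × weight|.

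**Every row against the stated dose.**

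| Weight (kg) | Tablets | mg | mg/kg, heaviest to lightest | Deviation | Nearest half-tablet step |
|---|---|---|---|---|---|
| 41–50 | 0.5 | 7.5 | 0.150–0.183 | −40% to −27% | 0.5 below 45 kg, 1.0 above |
| 51–60 | 1.0 | 15 | 0.250–0.294 | 0% to +18% | 1.0 throughout |
| 61–70 | 1.0 | 15 | 0.214–0.246 | −14% to −2% | 1.0 throughout |
| 71–84 | 1.5 | 22.5 | 0.268–0.317 | +7% to +27% | 1.0 below 75 kg, 1.5 above |
| 85–100 | 2.0 | 30 | 0.300–0.353 | +20% to +41% | 1.5 throughout |

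The stated dose is reproduced at 60 kg (15 ÷ 60 = 0.250). It is not reached anywhere in the top row.

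**The top row in detail.**

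- 85 kg: target 0.25 × 85 = 21.25 mg. Two tablets: 30 ÷ 85 = 0.353 mg/kg (+41.2%, 8.75 mg over). 1.5 tablets: 22.5 ÷ 85 = 0.265 mg/kg (+5.9%, 1.25 mg over).
- 90 kg: target 22.5 mg. Two tablets: 0.333 mg/kg (+33.3%). 1.5 tablets: exactly 0.250 mg/kg.
- 100 kg: target 25.0 mg. Two tablets: 30 ÷ 100 = 0.300 mg/kg (+20.0%, 5.0 mg over). 1.5 tablets: 0.225 mg/kg (−10.0%, 2.5 mg under).

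**Where two tablets would be right.** The midpoint between 22.5 and 30 mg is 26.25 mg, so two tablets become the nearer step only above 26.25 ÷ 0.25 = 105 kg. Measured by ratio instead of difference, the switch is at √(22.5 × 30) ÷ 0.25 = 103.9 kg. Thirty milligrams equals 0.25 mg/kg only at 120 kg. All three weights lie outside the table.

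**The companion drug in the same row.** Section 5.1.2 quotes a "therapeutic dose range between 2–10 mg/kg/day dihydroartemisinin and 16–26 mg/kg/dose piperaquine". Five DHA-PIP tablets give 40 × 5 ÷ 100 = 2.00 to 40 × 5 ÷ 85 = 2.35 mg/kg DHA, and 320 × 5 ÷ 100 = 16.00 to 320 × 5 ÷ 85 = 18.82 mg/kg piperaquine. Both are inside the quoted ranges, so the misfit in this row is confined to the primaquine column.

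**The case against.** The strongest reply is that the stated dose is only approximate and no tolerance is set, so no written limit is breached. The nearest half-tablet step is a reviewer's criterion, not the protocol's. This stands in part: how far the word stretches is a judgement. It explains rounding that the tablet size forces, but not passing over a closer step that the table already uses one row above.

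A second reply is uneven treatment. The 41–50 kg row is 27–40% low, a departure of similar size, and 1.5 tablets at 75 kg would also give 0.300 mg/kg. Both facts are correct. The low row is not in the direction of the haemolysis risk, and its entry is the nearest step for part of its band. But correcting only the top row would leave the table short of the stated dose at the light end.

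Third, section 5.1.2 says that "This drug regimen has been used in mass drug administrations in more than 10,000 participants". It does not say that these weight bands were used, so it does not settle whether the experience covers 0.30–0.35 mg/kg.

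Fourth, other protections exist. Section 4.3.3 excludes "Any medical condition that in the judgment of the investigator would make the administration of the antimalarial treatment unsafe" and also "Any abnormal baseline laboratory screening tests: ALT, AST, creatinine, haemoglobin, platelet count, total WBC, out of normal range". Haemoglobin is checked at Day 7 of each round and at Month 3. Groups 4, 6 and 7 have adverse-event visits on Days 1 and 2 after dosing. Rule 7.2(f) withdraws from further vaccination a participant with a Grade 3 laboratory event related to vaccination. These limit the consequences but do not reconcile the row with the text.

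A reader might infer that the top band is unsafe, or that the absence of G6PD testing is a separate defect. The documents support neither. Nothing in them shows harm at 0.30–0.35 mg/kg, and omitting the test follows from the protocol's own low-dose rationale.

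**Conclusion.** The point holds as a mismatch between table and text. At 85–100 kg the table delivers 0.300–0.353 mg/kg, which is 20–41% or 5.0–8.75 mg above the stated dose, and it is the only row whose entry is not the nearest half-tablet step at any weight in its band. The row also exceeds the dose for which the protocol asserts safety in severe G6PD deficiency. That is a gap in the wording of the assurance, not a demonstrated hazard.

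The conclusion assumes that 0.25 mg/kg is the intended target and that half tablets can be given, as the table itself shows. At most 90 of the 190 participants receive primaquine (Groups 4, 6 and 7, 30 each). How many weigh 85–100 kg cannot be known from the document. No endpoint or sample-size figure is shown to be affected.

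Two minor notes do not carry the point. At 71–74 kg, 1.5 tablets give 0.304–0.317 mg/kg, where one tablet (0.203–0.211 mg/kg) is nearer. At 81–84 kg, four DHA-PIP tablets fall 1.2–4.8% below the quoted lower limits (81 kg: 1.975 and 15.80 mg/kg; 84 kg: 1.905 and 15.24 mg/kg).

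**What to change.** Change the primaquine entry for 85–100 kg from 2.0 to 1.5 tablets (22.5 mg, 0.225–0.265 mg/kg).

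If the table is kept as it is, replace the single approximate figure in 4.7.3 and 5.1.2 with the range the table delivers, 0.15–0.35 mg/kg, which covers both the 41–50 kg and the 85–100 kg rows. Limit the G6PD safety sentence to doses it can support. Even with the entry corrected, the table would run from 0.150 mg/kg (50 kg) to 0.317 mg/kg (71 kg), so stating the delivered range would still help.

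The cost is one table entry or a few words in two sections. A change to a prescribed dose is an amendment needing the approvals in section 11.3. No extra participants, visits or tests are required.

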4.8 Study Procedures

Procedures will be performed at the time points indicated in the schedule of procedures (Appendix A). Additional procedures or laboratory tests may be performed, at the discretion of the investigators if clinically necessary (e.g. follow up repeat haematology or biochemistry laboratory tests in the event of clinically significant abnormal results).

4.8.1 Recruitment of volunteers

Volunteers will be recruited using methods traditionally employed by the healthy volunteer unit of the Mahidol-Oxford Tropical Medicine Research Unit. The volunteer unit maintains a register of candidates who expressed interest in the past to participate in clinical trials. In addition volunteers will be recruited via flyers displayed and distributed in the University Hospital and among students attending the university.

4.8.2 Informed Consent

The informed consent process: trained study personnel will explain the purpose of the study according to the information sheet prior to any study related procedures being undertaken. The participant must personally sign and date the latest approved version of the informed consent form before any study specific procedures are performed. In such cases where the participant is illiterate, informed consent will be conducted in the presence of an impartial witness and the impartial witness would sign and date the informed consent form, while the participant provides their thumbprint.

The information sheet and informed consent form will be explained to the participants detailing no less than: the exact nature of the study; the implications and constraints of the protocol; the known side effects and any risks involved in taking part. The aims of the study and all tests to be carried out will be explained. It will be clearly stated that participation is entirely voluntary and that refusing to participate will not involve any penalty or affect the patients' right to receive standard medical care at the healthcare post. It will also be emphasized that if they do consent to participate and are enrolled, that they are free to withdraw from the study at any time, for any reason, without any penalty or prejudice to future care, and with no obligation to give the reason for withdrawal. The volunteers will have the opportunity to question the Investigator, or other independent parties to decide whether or not they will participate in the study.

Written informed consent will then be obtained by means of participant dated signature or thumbprint and witness dated signature, in the case of an illiterate participant, and dated signature of the person who presented and obtained the informed consent. The person who obtained the

consent must be suitably qualified and experienced, and have been authorized to do so by the study site Principal Investigator. A copy of the signed Informed Consent and Information Sheet will be given to the participants. The original signed form will be kept in the investigator's site file and retained at the study site.

Hospital consent for HIV test will be obtained prior to counselling and HIV test. Pre and post counselling for HIV screening, report and treatment for volunteer will be conducted with the support of certified staff from the Bangkok Hospital of Tropical Diseases. In case a participant is found to be HIV positive, follow up measures including but not limited to providing counselling and treatment according to standard hospital procedure will be arranged through certified staff from the Hospital for Tropical Diseases.

